13.2 Respiratory function testing (handheld ASMA-1 device)

PEF and FEV1 will be presented as non-normalized values and as percent predicted (see equations in 12.1.1). Information of use of respiratory aid (Bi-Pap) will be given in the data listings.

13.3 Muscle strength and motor function testing

13.3.1 Hand-Held Myometry (HHM)

Knee extension, knee flexion, elbow extension and elbow flexion, measured in Newton units will be presented separately for right and left side. Also, total lower limb score and upper limb score as the sum of extension and flexion results, will be summarized. Upper limb results will also be presented by dominant side. Normalized values (as percentage of normal HHM) will be given for both extension and flexion results. For normalization, the HHM results will be scaled by weight (i.e. knee flexion (N)/ weight (kg)). Average normal HHM values scaled by weight presented by Beenakker (2001) will be used as reference for children aged 4-16. For adults the following formulas from NIH, previously presented by Bohannon (1997), for normalization will be used:

Knee flexors	No formula for adults
Knee extensors (KE) %p, Female	Dominant side: $((KE/weight)/(465.22-84.7-(4.803*age) + (0.325*(4.4482216*weight))))*100$ Non-dominant side: $((KE/weight)/(480.7-95-(4.868*age)+(0.31*(4.4482216*weight))))*100$
Knee extensors (KE) %p, Male	Dominant side: $((KE/weight)/(465.22-(4.803*age) + (0.325*(4.4482216*weight))))*100$ Non-dominant side: $((KE/weight)/(480.7-(4.868*age) + (0.31*(4.4482216*weight))))*100$
Elbow flexion (EF) %p, Female	Dominant side: $((EF/weight)/(188.36-96.5-(0.61*age) + (0.14*(4.4482216*weight))))*100$ Non-dominant side: $((EF/weight)/(188.25-89.2-(0.65*age)+(0.132*(4.4482216*weight))))*100$
Elbow flexion (EF) %p, Male	Dominant side: $((EF/weight)/(188.36-(0.61*age) + (0.14*(4.4482216*weight))))*100$ Non-dominant side: $((EF/weight)/(188.25-(0.65*age) + (0.132*(4.4482216*weight))))*100$
Elbow extensors (EE) %p, Female	Dominant side: $((EE/weight)/(156.49-73-(1.032*age) + (0.116*(4.4482216*weight))))*100$ Non-dominant side: $((EE/weight)/(150.37-71.5-(1.044*age)+(0.126*(4.4482216*weight))))*100$
Elbow extensors	Dominant side: $((EE/weight)/(156.49-(1.032*age))$

(EE) %p, Male	$+(0.116*(4.4482216*weight))) * 100$ $\text{Non-dominant side: } ((EE/weight)/(150.37 - (1.044*age) + (0.126*(4.4482216*weight)))) * 100$
---------------	---

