Congenital Muscular Dystrophy Ascending Multiple Dose Cohort Study anaLyzing Pharmacokinetics at three dose Levels In Children and Adolescents with Assessment of Safety and Tolerability of Omigapil (CALLISTO)

National Institute of Neurological Disorders and Stroke
Reducing the burden of neurological disease...

Clinical Research Protocol

Abbreviated Title: CALLISTO
NIH Protocol Number: 15-N-0018
Santhera Protocol Number: SNT-I-015
Date of This Submission/Version (*see header*)
IND Number: 113,370
Eudract Number: 2012-002700-40
Compound: Omigapil Hydrogen Maleate
CRADA 2012-0097 (expiration 2020)

Confidential
Property of Santhera Pharmaceuticals (Switzerland) Ltd.

Synopsis

Study Title	Congenital Muscular Dystrophy Ascending Multiple Dose Cohort Study analyzing Pharmacokinetics at three dose Levels In Children and Adolescents with Assessment of Safety and Tolerability of Omigapil
Study Number	SNT-I-015
Study Phase	1
Study Acronym	CALLISTO
Planned Study Duration	84 weeks (16 weeks recruitment, 68 weeks study conduct). The above duration is assuming cohorts are dosed in staggered parallel. Patient participation will be up to 28 weeks (up to 4 weeks screening, 4 weeks run-in, 12 weeks treatment and a follow-up visit 8 weeks post last dose taken)
Investigational Product Dosage and Route of Administration	Omigapil oral solution (0.1 and 0.25 mg/ml in Humco [®] Cherry Syrup) Dosage: 0.02, 0.08 and 0.2 mg/kg/day; maximum daily dose: 5 mg Oral administration once per day after breakfast
Vehicle	Humco [®] Cherry Syrup
Indication	Congenital Muscular Dystrophy (CMD)
Study Objectives	
• The primary objective is to establish the pharmacokinetic profile of omigapil at a range of doses in pediatric and adolescent patients with CMD• The secondary objective is to evaluate the safety and tolerability of omigapil at a range of doses in pediatric and adolescent patients• The tertiary objective is to establish the feasibility of conducting disease-relevant clinical assessments in pediatric and adolescent patients with CMD to aid in the design of future studies

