Study Endpoints	
• The Primary Endpoint is the pharmacokinetic profile of omigapil and metabolites quantified by C_{max}, C_{min}, t_{max}, $t_{1/2}$, AUC_{0-t}, AUC_{0-8h}, AUC_{0-24h}, λ_z (terminal phase rate constant) and R_o (the extent of accumulation in plasma)• The Secondary Endpoint is safety and tolerability of omigapil at the doses tested, established through the collection of Adverse Events (AEs) and Serious Adverse Events (SAEs), vital signs, oxygen saturation, standard lab parameters and electrocardiogram (ECG) assessments.• The Tertiary Endpoint is the outcome of disease-relevant clinical assessments.
• Hospital-based pulmonary function tests (PFTs) by standard spirometry.• Home-based pulmonary function tests using a child-compatible hand-held device (ASMA-1).• Hospital-based evaluation of muscle strength & function.• Motor function scales.

- Time tests (ambulatory patients only).
- Functional Scales.
- Muscle Imaging (Muscle magnetic resonance imaging (MRI) and Muscle Ultrasound)
- Collection of biomarkers

Number of Centers

1

Number of Subjects
Patient Population

Approximately 20 eligible patients will be randomly assigned to ensure a minimum of 16 patients who have completed all study procedures (3 cohorts of 4, 4, and 8-12 patients)

Inclusion Criteria

- Ambulatory and non-ambulatory patients from age 5 - 16 years (≥ 5 years old and < 17 years old) at time of screening with a clinical picture (see below) consistent with COL6-related dystrophy (COL6-RD) or LAMA2-related dystrophy (LAMA2-RD)
- Under regular review at a neuromuscular center
- On adequate double-barrier contraception (if of child-bearing potential (CBP))
- Stable on any allowed concomitant medications for 1 month prior to run in phase
- Forced Vital Capacity (FVC) 30-80% of the predicted value and confirmed at Screening and Baseline visit(s)

For patients with Collagen VI-related dystrophy (COL6-RD)– required clinical picture

- Muscle weakness: inability to walk or, if patient is still ambulatory, inability to run and > 5 s for 10 m walk

Genetics and Pathology:

- Molecular diagnosis of COL6-RD, defined by one dominant or two recessive mutation(s) in COL6A1, COL6A2 or COL6A3 known to cause the clinical picture,
OR

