- Histological diagnosis showing (i) absent or significantly decreased expression of collagen VI in muscle (overall reduction or basal lamina specific) or (ii) absent or significantly abnormal matrix in skin fibroblast culture

For patients with Laminin alpha 2 related dystrophy (LAMA2-RD) – required clinical picture

- Muscle weakness: Inability to walk; if patient is still ambulatory, inability to run and > 5 s for 10 m walk.

Genetics and Pathology:

- Either: 2 identified pathologic or probable pathologic mutations in LAMA2 gene
OR
- 1 identified pathologic or probable pathologic mutation in LAMA 2 gene with evidence of decrease in laminin alpha 2 staining on muscle or skin biopsy

OR

- Evidence of decrease in laminin alpha 2 staining on muscle or skin biopsy with matching clinical phenotype and no suspicion of alpha dystroglycanopathy (aDG-RD) (clinically or by staining on muscle biopsy)

Exclusion Criteria

- Use of any investigational drug other than the study medication within 12 weeks of study start.
- Recurrent hospitalization for chest infections in previous 2 years (≥ 2 per year)
- Patients with respiratory parameters (eg: low pulmonary function test value i.e. $<30\%$ predicted or need for daytime non-invasive ventilation) currently affected by short term medications, or acute illness/ conditions (conduct baseline assessments when the patient has recovered and is no longer taking acute medication)
- Any need for surgery (i.e. scoliosis, gastrostomy, other) in the preceding 24 weeks or foreseen during the course of the study.
- Patient has an intercurrent significant medical condition or situation which in the opinion of the Investigator or the study Medical Monitor may put the patient at significant risk, confound the study results or interfere significantly with the patient's participation in the study.
- Failure to thrive, defined as:
 - Falling 20 percentiles (20/100) in body weight in the 12 weeks preceding Screening/Baseline (based on family report of weight loss and review of relevant medical records)
 - In patients below the 3rd percentile, any further drop in body weight percentile in the 12 weeks preceding Screening/Baseline (based on family report of weight loss and review of relevant medical records)
- Weight less than 17 kg at Baseline
- Morbidly obese or grossly overweight (≥ 86 percentile body mass index (BMI) in children)
- History of epilepsy or on antiepileptic medication at Screening/Baseline
- Diabetes

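### The adult hand-held myometry formulas in SAP 13.3.1 mix units: weight in kg is multiplied by the pound-to-newton factor, and measured and predicted strength are on different scales

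*SAP*

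**What the plan says.** SAP 13.3.1 covers knee and elbow extension and flexion, "measured in Newton units will be presented separately for right and left side". For percent of normal, "the HHM results will be scaled by weight (i.e. knee flexion (N)/ weight (kg"). Published average values, also scaled by weight, "will be used as reference for children aged 4-16".

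For adults the section lists 12 formulas: knee extension, elbow flexion and elbow extension, by sex and by dominant or non-dominant side. Female knee extension, dominant side, contains "KE/weight)/(465.22-84.7-(4.803*age) + (0.325*(4.4482216*weight))))*100". Male and female elbow flexion, dominant side, use "0.14*(4.4482216*weight" in the same position. The constant 4.4482216 stands in all 12. The section names no second weight variable and gives no instruction to convert kg to pounds.

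The protocol synopsis fixes who can reach these formulas. It admits "Ambulatory and non-ambulatory patients from age 5 - 16 years (≥ 5 years old and < 17 years old) at time of screening" and states that "Patient participation will be up to 28 weeks". The only weight limit in kg is an exclusion: "Weight less than 17 kg at Baseline".

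**The concern.** The number 4.4482216 is newtons per pound-force. Multiplying by it gives body weight in newtons only when weight is in pounds; for kg the factor is 9.80665. Within one formula the same variable is therefore kg in the numerator, where the section says so, and would have to be pounds in the denominator. A programmer who follows the SAP will enter kg in both places.

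The same formulas have a second inconsistency. The measured force is divided by weight and the predicted force is not, so the ratio does not compare like with like.

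At stake is the percent-of-normal myometry of any patient who moves from the paediatric reference to these formulas during the study. SAP section 13 reports changes from baseline where feasible. A switch of reference would then show as a change in strength with no change in measured force, and in a cohort of 4 one such value moves the mean visibly.

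**Working it through.** The documents give no worked value for these formulas, so there is no stated figure to reproduce. The check evaluates the formulas directly.

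**Inputs.** Coefficients are from SAP 13.3.1. Age is 17, the first age above the paediatric reference. Weights of 40–60 kg are an assumption, because the documents give only the 17 kg minimum; 17–70 kg is shown as a wider range. The male dominant elbow-extension line is evaluated as if bracketed like the other 11 (see step 5).

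**Step 1: the factor.** 9.80665 / 4.4482216 = 2.205. With kg entered, the body-weight term is too small by this factor.

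**Step 2: one formula in full.** Female knee extension, dominant side, age 17, 50 kg:

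- Terms without weight: 465.22 − 84.7 − 4.803 × 17 = 298.87
- Prediction as printed: 298.87 + 0.325 × 4.4482216 × 50 = 298.87 + 72.28 = 371.2
- Prediction with 9.80665: 298.87 + 0.325 × 9.80665 × 50 = 298.87 + 159.36 = 458.2
- Ratio: 458.2 / 371.2 = 1.235, so the constant alone inflates the percentage by 23.5%

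**Step 3: the constant alone, all formulas.** Inflation of percent of normal at age 17, taking the smallest and largest value over both sides and 40–60 kg:

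| | Female | Male |
|---|---|---|
| Knee extension | 18.6–27.1% | 14.7–22.2% |
| Elbow flexion | 25.4–37.9% | 14.1–20.9% |
| Elbow extension | 28.7–42.8% | 15.6–24.4% |

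The extremes are male elbow flexion, non-dominant, 40 kg (229.0 / 200.7 = 1.141) and female elbow extension, non-dominant, 60 kg (135.3 / 94.8 = 1.428). Over all 12 formulas the inflation is 6.4–16.2% at 17 kg and 22.7–47.1% at 70 kg. These ratios do not change if both predictions are divided by weight.

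**Step 4: the formula as printed.** Take a person whose force equals the 9.80665-based prediction, who should score 100%. In the case of step 2 the printed formula gives (458.2 / 50) / 371.2 × 100 = 2.47%. Across the 12 formulas the result is 2.0–3.3% at 40–60 kg and 1.8–6.8% at 17–70 kg. Replacing the constant and nothing else gives 100 / weight: 2.5% at 40 kg, 2.0% at 50 kg, 1.7% at 60 kg.

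**Step 5: one line with different brackets.** In male elbow extension, dominant side, the text available for review closes the denominator after the age term. Read literally, the weight term is then added outside the division. At 50 kg it contributes 0.116 × 4.4482216 × 50 = 25.8, or 2,580 percentage points. The line may have been broken in the conversion from PDF, so it needs a check against the signed SAP.

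**Step 6: who is reached.** Age below 17 at screening plus 28/52 = 0.54 years puts every patient below about 17.5 years at the last visit.

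**The case against.** **The printed percentage is not overstated.** A reader might infer from the constant that reported percent of normal will be 14–43% too high and will jump upward when a patient switches reference. The documents do not support that. With the measured force divided by weight and the prediction not, the printed result collapses to a few percent. The 14–43% is the effect of the constant in isolation, or what remains once the scale is put right. This part of the objection stands in full. For the same reason, replacing the constant alone is no remedy.

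**The unit of the source regression is not visible.** The SAP takes the formulas from an adult reference it cites and does not state the unit of the weight predictor. That the prediction needs body weight in newtons is inferred from the constant. If the term was built for pounds, the constant is right and the fault is a missing conversion. This stands as a limit on the diagnosis. The contradiction with the kg stated in the same section remains either way.

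**It may reach nobody.** The SAP calls these formulas adult formulas and never says that a 17-year-old is an adult. Its non-adult spirometry equations in 13.1 run to age 18 for females and 20 for males, and the adult strength reference is titled for ages 20 to 70. If adult means 18 or over, no participant gets there. This stands as a limit on impact. Yet a patient who turns 17 on study falls outside the 4–16 reference, and these are the only other formulas given.

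**The stakes are low.** Myometry is a tertiary, descriptive feasibility measure. Newton values are presented as well, and the documents tie no test or dose decision to percent of normal. This also stands.

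**Conclusion.** The adult formulas are wrong as written and should be corrected, with small expected impact. Two independent faults are present.

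- **Unit:** with weight in kg, the body-weight term is 2.205 times too small. In isolation this inflates percent of normal by 14–43% at age 17 and an assumed 40–60 kg. The female maxima are 27% for knee extension, 38% for elbow flexion and 43% for elbow extension. Over 17–70 kg the range is about 6–47%.
- **Scale:** measured force is divided by weight and predicted force is not. This dominates the net result, which is about 2–3% for a person at predicted strength at 40–60 kg.

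The size of the unit fault rests on the assumed weights and on the inference that the prediction takes body weight in newtons. The reach is limited to patients who pass age 16 on study and are then treated as adults. The documents give no age distribution, so the number of such patients cannot be derived from them.

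**What to change.** Make one edit to SAP 13.3.1:

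1. State the unit of weight in each term of each formula.
2. If weight is in kg, replace 4.4482216 by 9.80665. Otherwise convert kg to pounds and keep 4.4482216.
3. Put measured and predicted strength on the same scale: force over force, or both divided by weight.
4. Check the brackets of the male dominant elbow-extension line.
5. State which reference applies to a patient aged 17.
6. Verify one hand-worked case per formula, 12 in all, before programming.

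Items 2 and 3 belong together, since either alone leaves wrong percentages. The cost is a revised formula table, the matching change in the SAS code and a short hand check. No new data are needed.

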12.3 Other safety variables

ECG results (Heart rate, PR, QRS, RR, QT, QTcF and QTcB times) will be listed by dose level and summarized with descriptive statistics by dose level using absolute values and changes from baseline to post-baseline pre-dose values. Moreover, the changes within each visit from pre to post-dose will be summarized. The ECG interpretation (Normal, Abnormal but not clinically significant or Abnormal and clinically significant) and abnormal QTcF and QTcB results (values >500 ms or changes of >30 ms and of > 60 ms) will be listed by dose level and summarized by visit, time point and dose level as shift tables. The QTcF and QTcB times will be calculated based on the following formulas:

$$QTcF = QT / RR^{1/3}$$

$$QTcB = QT / RR^{1/2},$$

where $RR = 60 / HR$.

Vital signs results (ulna length, height based on ulna length, weight, saturation of peripheral oxygen, blood pressure, heart rate, respiratory rate, body temperature, ability to stand, ambulatory status) will be listed by dose level and summarized descriptively by visit, time point and dose level. Absolute values, changes from baseline to post-baseline pre-dose values and within visit changes from pre- to post-dose values will be presented in the summaries.

Liver abdominal ultrasound results (liver span, echogenicity, presence of cysts and tumours, bile duct dilatation, gallbladder filled, presence of stones and portal vein dilatation) will be listed by dose level and summarized descriptively by dose level and visit. For the last visit, information on changes in the ultrasound from baseline will be listed.

13 Disease relevant clinical assessments

All disease relevant clinical assessment variables will be summarized as data listings by dose level. In addition, descriptive statistics/ frequency tables will be included when appropriate. Both absolute values and changes from baseline (if feasible) will be presented. The descriptive statistics/ frequency tables will be broken down by visit. Relevant background status (age of the patient, ambulatory status and type of disease) and AUC_{0-24h} information from PK analysis of plasma concentrations vs time profiles of omigapil will be included in the listings.

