14.3.3 Muscle strength and motor function testing

Table 14.3.3.1 Descriptive statistics of Hand-Held Myometry

Table 14.3.3.2 Descriptive statistics of Goniometry results

Table 14.3.3.3 Descriptive statistics of Myogrip results

Table 14.3.3.4 Descriptive statistics of Jebsen Hand Function Test

Table 14.3.3.5 Descriptive statistics of Performance Upper limb assessment

Table 14.3.3.6 Descriptive statistics of North Star Ambulatory Assessment

Table 14.3.3.7 Descriptive statistics of Moviplate test score

Table 14.3.3.8 Descriptive statistics of Motor Function Measure

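### Eleven of the 12 adult hand-held myometry formulas divide force per kg by a prediction not divided by weight, so percent of normal is too small by a factor equal to body weight; the reference at age 17 is not stated

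*SAP*

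**What the plan says.** SAP 13.3.1 measures HHM in newtons and then normalises it: "For normalization, the HHM results will be scaled by weight (i.e. knee flexion (N)/ weight (kg" and so on. The child reference is on the same footing, being "Average normal HHM values scaled by weight". The section divides patients by age in one sentence: "will be used as reference for children aged 4-16. For adults the following formulas" follow.

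The adult table covers knee extension, elbow flexion and elbow extension, by sex and by dominant or non-dominant side, which makes 12 formulas. For knee flexors it states "No formula for adults". A typical entry is male dominant knee extension: "KE/weight)/(465.22-(4.803*age) + (0.325*(4.4482216*weight))))*100".

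The SAP reference list gives the adult source as covering ages 20 to 70. Section 13.3.1 gives no age at which a patient counts as an adult, and does not say whether age is taken at screening (as in SAP 8) or at the time of measurement (as in SAP 13.1 for the respiratory equations).

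The results feed "Table 14.3.3.1 Descriptive statistics of Hand-Held Myometry" in the table plan, and SAP 13 adds, for all clinical assessments, "Both absolute values and changes from baseline (if feasible) will be presented".

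**The concern.** A percentage of normal needs the observed and the reference value on one scale. The child rule meets this: N/kg over N/kg. The adult formulas keep N/kg on top, but below the line they have an intercept, an age term and a weight term, with no division by weight. If the denominator is in newtons, the result is the true percentage divided by the patient's weight.

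The adult formulas matter only if a participant can reach them. Entry is below 17 years at screening, and participation lasts up to 28 weeks with the feasibility assessments repeated up to Visit 6. A patient can therefore turn 17 on study, and the SAP names no reference for that age.

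If such a patient were moved to the adult formulas, percent of normal would drop to a few percent or less and look like near-total loss of strength. Knee flexion would lose its percent of normal altogether. With two of the planned cohorts at four patients, one such value could visibly shift a dose-level mean.

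**Working it through.** The documents give no worked result for these formulas, so there is no figure to reproduce. The check is internal: set the observed force equal to the formula's own prediction and see whether it returns 100%.

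**Inputs.** Formulas: SAP 13.3.1. Minimum baseline weight 17 kg, entry age below 17 and participation up to 28 weeks: protocol synopsis. Age 17 and weights of 30, 50 and 70 kg are assumed for illustration.

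**Step 1: the predictions.** Male dominant knee extension at 17 years and 50 kg:

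465.22 − 4.803 × 17 + 0.325 × 4.4482216 × 50 = 465.22 − 81.65 + 72.28 = 455.9

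All 11 intact formulas at 17 years and 50 kg:

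| Action | Sex | Dominant | Non-dominant |
|---|---|---|---|
| Knee extension | Female | 371.2 | 371.9 |
| Knee extension | Male | 455.9 | 466.9 |
| Elbow flexion | Female | 112.6 | 117.4 |
| Elbow flexion | Male | 209.1 | 206.6 |
| Elbow extension | Female | 91.7 | 89.1 |
| Elbow extension | Male | not counted | 160.6 |

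**Step 2: the unit of the denominator.** It is not printed. If these numbers were N/kg, a score of 100% at 50 kg would need between 89.146 × 50 = 4,457 N (female non-dominant elbow extension) and 466.891 × 50 = 23,345 N (male non-dominant knee extension). Only newtons fit.

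**Step 3: score at the predicted force.** With force = P, where P is the prediction, the printed formula gives (P/weight)/P × 100 = 100/weight. P cancels, so the result is the same for all 11 formulas at any age.

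| Weight | Score as printed | Correct score |
|---|---|---|
| 17 kg | 100/17 = 5.88% | 100% |
| 30 kg | 100/30 = 3.33% | 100% |
| 50 kg | 100/50 = 2.00% | 100% |
| 70 kg | 100/70 = 1.43% | 100% |

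**Step 4: an example.** Assume a male patient of 17 years and 50 kg with 150 N in dominant knee extension. As printed: (150/50)/455.9 × 100 = 0.66%. On matched scales: 150/455.9 × 100 = 32.9%.

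**Step 5: change over time.** A patient who stays at 50% of predicted while growing from 40 to 44 kg goes from 50/40 = 1.25% to 50/44 = 1.14%, through weight gain alone.

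**Step 6: who can reach the formulas.** 28 weeks is 28 × 7/365.25 = 0.54 years, so age on study stays below 17.54. A patient must be at least about 17 − 0.54 = 16.46 years old at screening to turn 17 before the last visit.

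**The twelfth formula.** Male dominant elbow extension, beginning "EE/weight)/(156.49-(1.032*age", is split across a table break, and its bracket appears to close before the weight term. That may come from text extraction, so it is left out of the count. Read like the others, its prediction is 164.7 and its score at predicted force is 2.00%.

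**The case against.** The strongest counter-argument is that no participant may ever meet these formulas. This is a paediatric and adolescent trial, and if an adult is someone of 18 or over, or 20 or over as in the cited source, the formulas are never used. The only general age definition in the SAP is age at the screening visit (SAP 8), and where age at measurement is wanted, the SAP says so. On that reading every patient falls within the child reference and there is no gap at 17. Reach may indeed be nil. The age reading is not conclusive, however: SAP 8 defines age as a baseline characteristic and does not mention HHM.

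A second point is that the newton figures depend on the unit of the weight term. If that term were meant in pounds (50 kg = 110.2 lb), the predictions at 17 years and 50 kg would rise by 17 to 38%, the range in step 2 would become 6,141 to 27,497 N, and the 32.9% in the example would become 27.6%. That is correct, and those figures hold only for the formulas as printed with weight in kg. The 100/weight result is unaffected, because the prediction cancels.

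Third, HHM is tertiary and descriptive, raw newtons are reported by side, and changes are presented only where feasible. All true, and this limits the consequence. It does not make the formulas right.

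**Conclusion.** The concern holds. As printed, 11 of the 12 adult HHM formulas return the true percent of normal divided by body weight. At the predicted force the score is 5.9% at 17 kg, the lowest weight eligible at baseline, and 1.4% at 70 kg, where it should be 100%. This follows from the algebra and rests on one inference, that the predictions are in newtons, which their size supports.

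The practical effect is limited. Only patients who turn 17 on study could be affected, and only if adult formulas start at 17 and age is taken at the visit; neither is written. If the adult formulas start later and age at visit is used, a 17-year-old has no stated reference at all. The number affected cannot be derived from the documents and may be zero. The correction is still worth making, because the SAP is the stated record of how endpoints were derived, and these formulas are wrong for anyone they are applied to.

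**What to change.** Put numerator and denominator on the same scale: newtons over predicted newtons, or both divided by weight. Either returns 100% at the predicted force in all 11 formulas. State which reference applies at age 17, and whether age for HHM is taken at screening or at the visit. Do not compute a change in percent of normal across a switch from the child to the adult reference. If the child reference is assigned to every patient, the adult formulas can simply be deleted.

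Two queries should be checked against the cited adult source or the original SAP file:

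- The factor 4.4482216 converts pound-force to newtons, while the only weight unit given in the section is kg. Confirm the unit of the weight term.
- Confirm the bracket in the male dominant elbow-extension formula.

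The cost is one formula correction and two definitions in the SAP. HHM percent-of-normal outputs need a rerun only for patients to whom the adult formulas were applied, and none if there are no such patients. The SAP states that its authors had access to the study data, so finding out is quick.
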